9.4.3.1. Analysis of Secondary Objectives

Secondary analyses will include descriptive statistics and tests of significance between pre- and post-MVC intensification. All significance tests will be two-sided and no adjustment for multiple comparisons will be made. If necessary due to assumption failures, appropriate non-parametric statistical tests will be applied.

1. Differences in the change in CD4+ T-cell absolute count and percentage from baseline to week 4 and baseline to week 24 will be compared descriptively via separate paired Student t-tests. Repeated CD4+ T-cell absolute count measured at different time points (3 historic time-points, baseline, week 4, and week 24) will be treated as the outcome variable in a linear mixed-effects model. The primary fixed effects will include time, period (MVC vs. pre-MVC), and interaction between time and period; random effects will include both intercept and slope allowing each subject to have individual starting CD4+ T-cell counts and rate of change. Baseline covariate adjustment will be included if necessary. A significant interaction term between time and period with positive coefficient will indicate if the rate of CD4 recovery is greater during MVC compared to pre-MVC.

2. Differences in the rate of CD4+ T-cell recovery (absolute count and percentage) during MVC intensification in subjects receiving a PI/r- vs. NNRTI-based regimen will be compared via the linear mixed effects model. The fixed effects will include time, regimen (PI/r vs NNRTI), and regimen-by-time interaction; random effects will include both intercept and slope. The regimen-by-time interaction term in the model will indicate the difference in CD4+ T cell recovery rates between the two regimen groups. Baseline covariate adjustment will be included if necessary.

3. Differences in gene expression profiles between subjects receiving a PI/r vs. NNRTI-based regimen at baseline and weeks 4 and 24 will be examined by comparing the gene lists generated in the primary analysis by regimen type. If necessary, statistical modeling will include a dichotomous variable to indicate regimen type.

4. Differences in the proportion of CD4+/CD8+ T-cell immune activation, maturation, regulatory and apoptosis markers between baseline and weeks 4 and 24 will be compared cross-sectionally via McNemar's test or paired t-tests as appropriate.

5. Association between change in early immune subsets and phase 2 CD4 recovery will be assessed via Pearson's correlation analysis.

6. MVC plasma to CSF ratios at weeks 4 and 24 will be reported via descriptive statistics. Differences in MVC concentration ratios between subjects receiving a PI/r- vs. NNRTI-based background regimen will be compared via McNemar's test or paired t-tests as appropriate.

7. Descriptive statistics of CNS markers of immune activation will be reported via descriptive statistics. Differences in CNS markers of immune activation between baseline and weeks 4 and 24 will be compared cross-sectionally via McNemar's test or paired t-tests as appropriate.

8. Association between change in CNS markers of immune activation and MVC plasma to CSF ratios will be assessed via Pearson's correlation analysis.

9. Descriptive statistics of toxicity/intolerance during MVC treatment intensification will be reported via descriptive statistics. Differences in proportions of grades > 2 laboratory abnormalities and signs and symptoms will be compared via McNemar's test between time points.

10. Virologic failure during MVC treatment intensification will be reported via descriptive statistics.

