3.0 STUDY DESIGN

3.1 Study Design (Main Study)

Thirty patients will be enrolled to evaluate the impact of adding the CCR5 inhibitor, MVC, to a stable suppressive HIV regimen on the rate of CD4+ T-cell recovery and gene expression profiles. At baseline whole genome expression (38,000 genes) profiles and extended flow cytometry will be performed on purified CD4+/CD8+ T-cells in all subjects. In addition, pre-MVC phase 2 CD4+ T-cell recovery rate will be estimated for each subject from historic laboratory data obtained during the 12 months prior to the baseline visit. All subjects will receive treatment intensification with MVC dose-adjusted to their background HIV regimen for 24 weeks. Regular visits will occur on weeks 2, 4, 8, 12 and 24 to assess efficacy, safety and medication tolerance. Additional microarray and

extended flow cytometric analyses will be performed at weeks 4 and 24 of MVC therapy. After 24 weeks of MVC treatment intensification, MVC will be discontinued, the original antiretroviral regimen will be maintained and subjects will return for a 12 week follow-up visit to evaluate on-going CD4+ T-cell recovery, continued HIV RNA suppression and any potential adverse events.

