3.4 Flow Cytometry for CD4 and CD8 T-cells

Measurements for CD4+/CD8+ subsets will be determined at screening, weeks 2, 4, 8, 12, 24 and 12 weeks post CCR5-intensification. In addition, extended phenotype characterization will be performed at baseline, pre-entry and weeks 4 and 24 to determine the proportion of CD4+ and CD8+ lymphocytes that are naive (CD45RA+), activated (CD38+/HLA-DR+) or, among CD4+ cells, regulatory (CD25+CD127-).

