6.1 Schedule of Events – Clinical Evaluations

	Screening	Pre-Entry	Entry	Maraviroc Therapy Intensification (24 weeks)					Post-Maraviroc Intensificatoin	Treatment Failure, Tox or Premature D/C
	Within 30 days of entry	> 48 hrs before entry	Day 0	Week 2	Week 4	Week 8	Week 12	Week 24	Week 36	
Informed Consent	X									
Medical/Medication History	X									
Documentation of HIV	X									
Clinical Assessment / AE			X	X	X	X	X	X	X	X
Documentation of within criteria HIV RNA and CD4 prior to screen labs	X									
Complete Physical Exam			X							X
Targeted Physical Exam							X	X	X	
Start and Dispense Drug			X		X		X			
Stop and Collect Drug								X		X
Concomitant Medications	X		X	X	X	X	X	X	X	X
Adherence Assessment	X		X	X	X	X	X	X	X	X

CCTG 590
Protocol version 1.0
August 13, 2008

Schedule of Events – Laboratory Evaluations

	Screening	Pre-Entry	Entry	Maraviroc Therapy Intensification (24 weeks)					Post-Maraviroc Intensification	Treatment Failure, Tox or Premature D/C
	Within 30 days of entry	> 48 hrs before entry	Day 0	Week 2 (± 1 wk)	Week 4 (± 1 wk)	Week 8 (± 2 wk)	Week 12 (± 2 wk)	Week 24 (± 2 wk)	Week 36 (± 2 wk)	
Hematology (local lab)	X		X	X	X	X	X	X	X	X
Prothrombin time (local lab) †	X									
Chemistry / LFT (local lab)	X				X		X	X	X	X
Pregnancy test (local lab)	X	And anytime when suspected								
CD4+/CD8+ (local lab)	X		X	X	X	X	X	X	X	X
§ CD4 ≤ 350; HIV RNA ≤ 50	X									
Plasma HIV-1 RNA PCR (local lab)	X		X		X			X	X	X
Plasma for MVC levels †			X		X			X		
Extended flow cytometry & PBMC collection (UCSD lab)		X	X		X			X		
Microarray - PBMCs collection (local processing in real-time)			X		X			X		
Lumbar puncture†			X		X			X		
Plasma for storage			X		X			X	X	
Serum for storage			X		X			X	X	
Ship ambient sample for extended flow in real-time		X	X		X			X		
Ship frozen all stored PBMCs, plasma and serum									X	
HIV Resistance & Tropism testing										X

§ If available within 30 days of screen then do not need to repeat laboratory test and can use value obtained within 90 days as screen value

† Only for subjects co-enrolled in the central nervous system sub-study

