6.3.2 Medical and Laboratory History

At screening a medical history will be obtained and must be recorded in the source documents. The medical history should include any previous HIV-related diagnoses and AIDS-defining events.

In addition, prior to obtaining screening laboratories, documentation of all historic plasma HIV-1 RNA load and CD4+ T-cell counts since initiation of first ARV regimen must be recorded in the source documents and on-line CRF form (www.cfar.ucsd.edu/intranet). **Of note:** a minimum of 3 CD4+ T-cell (below 350 cells/mm³) and HIV RNA values (below 50 copies/mL) obtained \geq 30 days apart must be obtained and recorded.

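### The CD4 slope model leaves out CD4 counts the study already holds (weeks 8 and 12 on MVC, and historic counts beyond three), with no rule for choosing the three

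*Combined protocol and SAP*

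**What the plan says.** Objective 1.2.1 and hypothesis 1b (section 2.3.1) compare the CD4 rate before and during MVC. Section 9.4.3.1, item 1, tests this with a linear mixed model whose data are listed as "3 historic time-points, baseline, week 4, and week 24) will be treated as the outcome variable in a linear mixed-effects model". Its structure is given as "The primary fixed effects will include time, period (MVC vs. pre-MVC), and interaction between time and period", with random intercept and slope. The decision rule is "A significant interaction term between time and period with positive coefficient will indicate if the rate of CD4 recovery is greater during MVC".

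More CD4 data are collected than the model uses.

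- **On MVC.** Section 3.4: "Measurements for CD4+/CD8+ subsets will be determined at screening, weeks 2, 4, 8, 12, 24 and 12 weeks post CCR5-intensification". The laboratory schedule in 6.1 agrees and adds the entry visit. Section 3.1 says of these visits: "Regular visits will occur on weeks 2, 4, 8, 12 and 24 to assess efficacy, safety and medication tolerance".
- **Before MVC.** Section 3.1 says the pre-MVC rate "will be estimated for each subject from historic laboratory data obtained during the 12 months prior to the baseline visit". Section 6.3.2 requires "documentation of all historic plasma HIV-1 RNA load and CD4+ T-cell counts since initiation of first ARV regimen must be recorded". Inclusion criterion 4.1.2 asks for at least three values, 30 or more days apart; three is a floor there, not a fixed number.

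Endpoint 9.2.2, item 1, names baseline and weeks 4 and 24, as the model does, without giving a reason. Section 6.2.1 (Entry) places the first dose after the entry blood draw. Section 9.4.3.1 does not say which period the entry count belongs to.

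**The concern.** A slope is estimated better from more counts spread over a longer time. If the entry count is pre-MVC, the on-MVC slope rests on two counts per subject although five are taken. On the historic side, a subject with more than three counts has some dropped, and the plan does not say which. Three counts that span the year estimate the earlier slope much better than three from its last months. With no rule, the selection could be made after the data are seen, in an analysis whose tests are unadjusted for multiplicity. What is at stake is the precision of the only test of objective 1.2.1, and one avoidable free choice in it.

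**Working it through.** **No plan figure to reproduce.** Section 9.3 gives power for gene expression only. No SD, alpha or effect size is stated for the CD4 slope, so the figures below are illustrative.

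**Inputs from the documents.** n = 30. Tests are two-sided. Visit weeks are as scheduled. The gain of 32 cells by 24 weeks is the meta-analysis figure cited in section 2.2.1.2 (Impact on CD4 Recovery), which comes from a different population.

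**Assumed.** Residual SD 40 cells (30 and 60 also shown), independent errors, alpha 0.05, normal approximation, the same schedule for every subject, and the entry count coded pre-MVC.

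**Effect.** One week is 7/30.44 = 0.230 month, so 24 weeks is 5.52 months. A linear gain of 32 cells is 32/5.52 = 5.80 cells/month.

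**Formula.** With equal schedules the random intercept and the common random slope cancel from the interaction, leaving

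Var = (SD²/n) × (1/S_pre + 1/S_on),

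where S is the sum of squared deviations of time within a period, in months². Power = Φ(5.80/SE − 1.96).

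**S_on** (week² × 0.230² gives month²):
- Weeks 4, 24 (mean 14): 100 + 100 = 200, or 10.58.
- Weeks 4, 8, 12, 24 (mean 12): 64 + 16 + 0 + 144 = 224, or 11.85.
- Weeks 2, 4, 8, 12, 24 (mean 10): 64 + 36 + 4 + 4 + 196 = 304, or 16.08.

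**S_pre** (months, entry at 0 included):
- −6, −4, −2, 0: 20.
- −12, −8, −4, 0: 80.
- −12 to −2 in steps of two, and 0: 112.
- −3, −2, −1, 0: 5.

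**Results.** SD²/n = 1600/30 = 53.33.

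| Historic counts (months) | On-MVC weeks | Variance | SE | Power |
|---|---|---|---|---|
| −6, −4, −2 (latest three of six) | 4, 24 | 53.33 × (1/20 + 1/10.58) | 2.78 | 55% |
| all six | 4, 24 | 53.33 × (1/112 + 1/10.58) | 2.35 | 69% |
| all six | 4, 8, 12, 24 | 53.33 × (1/112 + 1/11.85) | 2.23 | 74% |
| −12, −8, −4 | 4, 24 | 53.33 × (1/80 + 1/10.58) | 2.39 | 68% |
| −12, −8, −4 | 4, 8, 12, 24 | 53.33 × (1/80 + 1/11.85) | 2.27 | 72% |
| −12, −8, −4 | 2, 4, 8, 12, 24 | 53.33 × (1/80 + 1/16.08) | 2.00 | 83% |
| −3, −2, −1 | 4, 24 | 53.33 × (1/5 + 1/10.58) | 3.96 | 31% |
| −3, −2, −1 | 4, 8, 12, 24 | 53.33 × (1/5 + 1/11.85) | 3.89 | 32% |

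For the first three rows the same formula gives 80%, 91% and 93% at SD 30, and 29%, 38% and 41% at SD 60. If subjects also differ in their change of slope with SD 6 cells/month, add 36/30 = 1.2 to each variance; at SD 40 the three rows become 49%, 61% and 65%.

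**Why week 2 should not be in the main fit.** Take a gain that rises evenly to 32 cells at week 4 and then holds. The rate after week 4 is unchanged, so the interaction should be 0.
- Weeks 4, 24 or weeks 4, 8, 12, 24: every on-MVC count sits 32 above trend, so the interaction is 0.
- With week 2 (16 above trend): the cross-product is (−8 × 16) + (−6 − 2 + 2 + 14) × 32 = 128. The slope is 128/304 = 0.421 per week, or +1.8 cells/month. With SE 2.00 it is declared significant about 15% of the time.

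**Why the entry coding should be stated.** Use the same early gain with the planned visits, and code entry as MVC. The times are 0, 4 and 24 (mean 9.33, sum of squares 330.7) and the excesses 0, 32 and 32. The cross-product is 32 × (−5.33 + 14.67) = 298.7. The slope is 298.7/330.7 = 0.903 per week, or 3.9 cells/month, against 0 with entry coded pre-MVC.

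**The case against.** The planned visits are prespecified. They match endpoint 9.2.2, item 1, and the flow cytometry and microarray visits. Section 9.1 says the study is powered for gene expression. If CD4 is linear within each period, dropping visits costs precision but causes no bias. All of this stands. None of it is a reason for discarding counts already in the database, or for leaving the choice of three open.

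The gain is also uneven. If the three historic counts already span the year, further historic counts add about one point (68% to 69%). Weeks 8 and 12 alone add about four points (68% to 72%), and about two or fewer if residuals are serially correlated (assumed correlation 0.5 at one month, for half or all of the residual variance). If all the history is bunched just before entry, they add about one point. This stands too, and limits the size of the point.

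Three stronger readings are tempting.

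- **Adding every on-MVC visit lifts power from 68% to 83%.** The arithmetic is right, but most of the lift comes from week 2, the visit that lets an early gain pass for a change of rate.
- **The coding of the entry count is wide open.** The analysis section is silent, but 6.2.1 draws the entry sample before the first dose, which points to pre-MVC. With a purely linear gain both codings give 5.8 cells/month.
- **The undefined time origin is a defect.** It does not affect the tested coefficient. Moving the origin 12 months back leaves the interaction at 5.8 and changes only the period coefficient, by −12 × 5.80 = −69.6, and the plan draws no conclusion from that coefficient.

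**Conclusion.** The point holds as a matter of precision and of one missing selection rule. The model for objective 1.2.1 uses two of the five on-MVC counts and three unselected historic counts, with no reason given. In the illustrative case, power rises from 55% to 69% by using six historic counts instead of the latest three, and to 74% with weeks 8 and 12. The historic counts carry most of the gain, and only where subjects have more than three and the chosen three would not span the year. These figures rest on an assumed SD, spacing, error structure and effect. Schedules that differ between subjects, correlated errors or a t reference would move them.

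A reader might infer that the planned test is biased or that a figure in the plan is wrong. The documents support neither: the planned model is unbiased if its linear form holds, and no power is claimed for it. This is a secondary analysis in a pilot; the change is worth making because it is nearly free.

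**What to change.** In 9.4.3.1, item 1:

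- Fit the model to all CD4 counts recorded in the 12 months before entry, the entry count, and weeks 4, 8, 12 and 24. Keep the time-by-period interaction as the test.
- State that the entry count is coded pre-MVC, in line with the pre-dose draw in 6.2.1.
- Report the fit that also includes week 2 as a sensitivity analysis.
- If the sponsor prefers the restricted set, give the reason and a rule, fixed in advance, for which three historic counts enter.

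Align endpoint 9.2.2, item 1, with the visits used. Reading the period coefficient as an early shift above the projected pre-MVC trend is optional; if it is done, time should be measured from entry.

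The cost is wording in two sections and one extra model fit. No visit, sample or assay is added.

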1.0 STUDY OBJECTIVES

1.1 Primary Objectives

1.1.1 To characterize changes in gene expression profiles associated with early (week 4) and late (week 24) MVC therapy intensification.

1.1.2 To evaluate the association of gene expression profiles induced by MVC on the rate of CD4+ T-cell recovery during MVC therapy intensification.

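### The CD4 mixed model assumes MVC changes every subject's slope equally; if the change varies between subjects, the standard error of the time-by-period interaction is somewhat too small

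*Combined protocol and SAP*

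**What the plan says.** Item 1 of section 9.4.3.1 fits one linear mixed model to the CD4 counts before and during MVC. The outcome is "Repeated CD4+ T-cell absolute count measured at different time points (3 historic time-points, baseline, week 4, and week 24", six counts per subject. The fixed part is stated as "The primary fixed effects will include time, period (MVC vs. pre-MVC), and interaction between time and period", and for the random part "random effects will include both intercept and slope allowing each subject to have individual starting CD4+ T-cell counts and rate of change". The conclusion is drawn from one term: "A significant interaction term between time and period with positive coefficient will indicate if the rate of CD4 recovery is greater during MVC".

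The section names no random period or time-by-period effect, no robust variance and no small-sample method. It adds that "All significance tests will be two-sided and no adjustment for multiple comparisons will be made". It gives no alpha for the secondary tests and no residual SD, power or standard error for this model. Section 3.1 takes the pre-MVC rate from "historic laboratory data obtained during the 12 months prior to the baseline visit" and sets the sample at 30 subjects in a single arm.

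**The concern.** The quantity tested is a within-subject change in slope. A single random slope lets subjects differ in their overall rate, but the gap between a subject's on-MVC and pre-MVC rates is then the same for everyone.

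Other parts of the protocol lean the other way. Primary objective 1.1.2 is "To evaluate the association of gene expression profiles induced by MVC on the rate of CD4+ T-cell recovery during MVC therapy intensification". Section 2.3.1 ties recovery on MVC to gene profiles, activation and apoptosis markers, naive cells and background regimen. Item 5 of section 9.4.3.1 correlates early subset change with CD4 recovery. If MVC helps some subjects more than others, part of the uncertainty in the mean slope change is left out of its standard error. The confidence interval is then too narrow, and the significance criterion is met too often when the mean change is zero. This model is the plan's formal test of secondary objective 1.2.1.

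**Working it through.** There is no stated figure to reproduce: the power table in section 9.3 concerns gene expression.

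**Inputs from the documents.** n = 30; three historic counts, baseline, week 4 and week 24; fixed time, period and time-by-period; random intercept and one slope.

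**Assumptions.** Two-sided alpha 0.05; residual SD σ of 30 to 60 cells; SD of slope change between subjects τ of 0 to 12 cells/month; intercept SD 60; pre-MVC slope SD 3 cells/month (values of 1 and 5 gave the same results); historic counts at months −9, −6 and −3. Weeks 4 and 24 are months 0.92 and 5.52. Baseline is taken in turn as pre-MVC and as MVC, because item 1 does not say which.

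**Scale.** Section 2.1 gives average phase 2 rates of 2 to 10 cells/mm³ per month. The meta-analysis cited in the section on CD4 recovery gives +32 cells at 24 weeks: 32 / 5.52 = 5.8 cells/month.

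**True variance.** With the same times for every subject, the interaction estimate is the mean of the 30 subject-level least-squares slope differences, whichever of these covariances is used. Its variance is

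(cσ² + τ²) / 30,

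where c is the diagonal element of (X′X)⁻¹ for the interaction: 0.117 with baseline as pre-MVC, 0.113 with baseline as MVC.

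**Variance the written model reports.** The single random slope adds nothing to the variance of the interaction, so τ enters only by inflating the fitted residual. The best-fitting residual variance is σ² + qτ². Here q is the sum of squares of max(t, 0) left after regression on an intercept and t, divided by 4; it is 2.56. The reported variance is therefore

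(cσ² + kτ²) / 30, with k = c × q = 0.30 (0.117 × 2.56) or 0.29 (0.113 × 2.56).

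About 30% of the τ² term is counted.

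**Type I error** = 2Φ(−1.96 × model SE / true SE). Example with σ = 30, τ = 5, baseline as MVC: model SE = √[(101.4 + 7.2)/30] = 1.90; true SE = √[(101.4 + 25)/30] = 2.05; ratio 0.927; type I error 6.9%.

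| τ (cells/month) | σ = 60, baseline pre-MVC: model SE / true SE | Type I error | σ = 30, baseline MVC: model SE / true SE | Type I error |
|---|---|---|---|---|
| 0 | 3.74 / 3.74 | 5.0% | 1.84 / 1.84 | 5.0% |
| 3 | 3.76 / 3.78 | 5.2% | 1.86 / 1.92 | 5.7% |
| 5 | 3.78 / 3.85 | 5.5% | 1.90 / 2.05 | 6.9% |
| 8 | 3.83 / 4.02 | 6.2% | 2.00 / 2.35 | 9.5% |
| 12 | 3.93 / 4.34 | 7.6% | 2.18 / 2.86 | 13.5% |

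**Other historic dates.** At months −12, −8 and −4, c is 0.107 (baseline pre-MVC) or 0.088 (baseline MVC). The worst case (σ = 30, τ = 12, baseline MVC) gives 1.98 / 2.73, a ratio of 0.726 and type I error of about 15.5%.

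**Simulation check** (REML, 400 trials, months −12, −8 and −4, σ = 20, τ = 5, baseline pre-MVC). The empirical SD of the estimate was 1.52 under every analysis.

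| Analysis | Mean SE | Type I error |
|---|---|---|
| Written model | 1.29 | 10.2% (z), 8.5% (t, 29 df) |
| Random time-by-period slope added | 1.49 | 7.0% (z), 5.8% (t, 29 df) |
| One-sample t-test on slope differences | 1.48 | 6.2% |

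With τ = 0 the written model gave 5.5%. Monte Carlo error is 1 to 1.5 points. This σ lies below the range used in the main table, so the run checks the mechanism and does not set the size. In a separate check, the slope-difference t-test held 4.7 to 5.6%.

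**The case against.** The strongest reply is that nothing in the documents fixes the size. Neither σ nor τ is given, and τ = 12 is four times the assumed pre-MVC slope SD and about twice the expected effect of 5.8 cells/month. At τ of 3 to 5 the type I error is 5.2 to 6.9%. If no subject's slope changes, the written model is correct. The test is secondary, unadjusted for multiplicity, and belongs to a study that section 9.1 calls a pilot powered on gene expression. All of this stands and limits the point.

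It is also fair that objective 1.1.2 and item 5 speak of the rate of recovery, and a random slope does let rates differ. A reader might infer that the protocol states that the slope change differs between subjects; it does not. But under the written model, on-MVC rates can differ only as much as the pre-MVC rates already did. That sits poorly with a search for MVC-induced profiles that go with better recovery. Heterogeneous change is a plausible inference, and the analysis should allow for it.

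Two stronger readings are not supported. One is that the estimated slope change is biased: in complete balanced data it is unchanged, and only the standard error, interval and p-value are affected. The other is that the extra CD4 counts scheduled in section 6.1 (weeks 2, 8 and 12) add to the problem: item 1 does not put them in this model.

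Finally, the fuller model may be hard to fit. With σ = 45 and τ = 5, 22 of 40 REML fits failed to converge or hit a boundary. A fallback is therefore needed.

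**Conclusion.** The point holds conditionally. As written, the model imposes one common slope change. Whenever the change varies between subjects, the interaction's model-based standard error is too small, because only about 30% of that variation is counted under the historic dates used in the main table. For residual SDs of 30 to 60 cells, type I error at a nominal 5% runs from 5.0% (uniform change) through 5.5 to 6.9% (SD 5) to 7.6 to 13.5% (SD 12), or about 15.5% in the worst case with other historic dates. Alpha, both SDs and the historic dates are assumptions. A reader might infer that a positive result from this model would be spurious; the documents do not support that, since the inflation is small unless slope change varies widely relative to the noise in the counts. The impact is modest.

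**What to change.** In item 1, test the interaction in a model with an added random time-by-period slope and a named small-sample degrees-of-freedom method. Pre-specify what replaces it if the fit does not converge or reaches a boundary: a one-sample t-test on each subject's on-MVC minus pre-MVC slope, or a subject-clustered robust standard error with small-sample correction. State which period the baseline count belongs to; section 6.2.1 has the entry bloods drawn before the first dose.

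This is a cheap improvement and needs no new data. The costs are:
- **A wider interval when response varies.** It is about 2% wider at τ = 5, σ = 60, baseline pre-MVC (3.85 / 3.78), and about 31% wider at τ = 12, σ = 30, baseline MVC (2.86 / 2.18).
- **Possible non-convergence** of the fuller model, hence the fallback.
- **For the t-test, loss of subjects with incomplete counts.** If baseline is pre-MVC, the on-MVC slope needs both week 4 and week 24. With irregular historic dates the t-test also weights subjects differently from the mixed model.

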2.4.1 Hypotheses

1. Maraviroc (MVC) concentrations in CSF will approximate 24% of the plasma C_{min} and will vary across the dosing interval.
 - a. Subjects receiving background HIV therapy containing a PI/r will achieve higher CSF MVC concentrations than those receiving not receiving a PI/r
2. MVC treatment-intensification will decrease immune activation (activated T-cells and pro-inflammatory cytokines) in the CSF.
3. Among subjects with CSF viral replication above 2 copies/mL at baseline, all will be suppressed below 2 copies/mL after 4 weeks of MVC treatment-intensification.

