3.2 Study Design (CSF Sub-Study)

This is a sub-study of the MVC treatment-intensification protocol (i.e., a “piggyback” protocol). The primary eligibility criteria will be enrollment into the MVC parent study, ability to give informed consent to lumbar puncture (LPs), and the absence of medications or conditions that would contraindicate lumbar puncture (e.g., coagulopathy). Pre-treatment LPs will be performed, followed by a LP at week 4 of MVC treatment intensification (i.e., “steady state”). All LPs will be performed within one hour of a parent protocol-dictated blood draw, reducing the need for separate visits or additional phlebotomy. For subjects willing to undergo more than one LP, an additional LP will be performed at week 24 of MVC treatment intensification. The primary study outcomes will be measurement of MVC concentrations and reductions in markers of immune activation levels in CSF at week 4.

The study will aim to obtain 3 LPs in as many subjects as possible with the goal being at least two LPs separated by at least 4 weeks in up to 17 participants. After informed consent is obtained, subjects will undergo a brief screening to ensure the absence of contraindications to LP. If eligible subjects choose to enroll, subsequent visits will occur at major visits of the parent protocol (baseline, week 4 and 24). Based on prior experience we conservatively estimate that approximately 60% of subjects in the parent protocol will be willing to consent to lumbar puncture an average of 2.5 LPs per consenting subject. In total, we estimate that this CSF sub-study will yield approximately 43 LPs from individuals taking MVC. Post-dose timing of the lumbar punctures will be limited by the parent protocols but we will strive to vary the post-dose lumbar puncture interval in order to have approximately equal representation from two intervals.

- Interval 1: 2 - 6 hours post dose
- Interval 2: 6 - 12 hours post dose

If successful, this variation across the dosing interval will improve the accuracy of population pharmacokinetic modeling.

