9.2.2 Secondary

1. CD4+ T-cell absolute count and percentage at baseline, weeks 4 and 24.
2. The proportion of CD4+/CD8+ T-cell immune activation, maturation, regulatory and apoptosis markers at baseline and weeks 4 and 24.
3. Grades ≥ 2 laboratory abnormalities and signs and symptoms.
4. Paired plasma to CSF ratios of MVC concentration at week 4.
5. Soluble immune activation markers in CSF at baseline and week 4.
6. HIV RNA loads in CSF at baseline and week 4.

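### The CSF hypothesis is set against plasma Cmin, but item 6 summarises paired plasma:CSF ratios by week with no account of time since dose

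*Combined protocol and SAP*

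**What the plan says.** Section 2.4.1, hypothesis 1, expects that maraviroc "concentrations in CSF will approximate 24% of the plasma C_{min} and will vary across the dosing interval". Its denominator is the plasma trough. Hypothesis 1a adds that CSF concentrations will be higher with a PI/r background.

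Section 3.2 fixes how the samples are timed. "All LPs will be performed within one hour of a parent protocol-dictated blood draw", so each plasma value belongs to roughly the same time as its CSF value. The two planned windows are "Interval 1: 2 - 6 hours post dose" and "Interval 2: 6 - 12 hours post dose", and the balance between them is an aim: "we will strive to vary the post-dose lumbar puncture interval in order to have approximately equal representation from two intervals". The same section gives population PK modelling as the reason for the spread.

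Section 9.2.2, endpoint 4, is "Paired plasma to CSF ratios of MVC concentration at week 4". Section 9.4.3.1, item 6, states that "MVC plasma to CSF ratios at weeks 4 and 24 will be reported via descriptive statistics", and then compares the ratios between PI/r and NNRTI regimens by McNemar's test or paired t-tests. Section 9 has no Cmin, no comparison with 24%, no term or stratum for time post-dose, and no description of the PK model. Section 6.3.14 lists plasma maraviroc collections at baseline and weeks 4 and 24, with no separate trough sample.

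**The concern.** The hypothesis and the planned summary use different denominators. One is plasma at trough. The other is plasma at whatever time the lumbar puncture took place, which by design is often well before trough. A reader who sets the reported ratio beside 24% would be comparing two different quantities, and could judge the hypothesis wrong when it is right, or the reverse.

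A paired ratio can also change over the dosing interval, so its average depends on how many samples fall early and how many late. That affects the week 4 and week 24 summaries, the regimen comparison in item 6, and the correlation in item 8, which uses the same ratios.

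**Working it through.** **Inputs from the documents.** Target 24% of Cmin (2.4.1); windows 2-6 h and 6-12 h, about half each (3.2); twice-daily dosing (5.1.1), so trough is taken as 12 h; up to 17 subjects and an average of 2.5 LPs each (3.2).

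**The plan's own figures.** No derivation is given for 24%, and there is no precision calculation for the ratio, so neither can be reproduced. The sub-study size can be checked: 0.60 × 30 = 18 against 17 stated, and 17 × 2.5 = 42.5 against about 43 stated. Both agree closely enough.

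**Step 1: definitions.** With C(t) the plasma level at time t,

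CSF(t)/C(t) = [CSF(t)/Cmin] × [Cmin/C(t)].

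The two ratios agree only where C(t) = Cmin, that is, with flat plasma or at trough. This step needs no PK assumption.

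**Step 2: size, under assumptions.** Assume that plasma is log-linear from 2 to 12 h with C(2 h)/C(12 h) = k, that CSF is constant at 0.24 × Cmin, and that sampling is uniform within each window. With λ = ln(k)/10, the mean paired CSF:plasma ratios are:

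- 2-6 h: 0.24 × (k^-0.6 − k^-1)/(4λ)
- 6-12 h: 0.24 × (1 − k^-0.6)/(6λ)

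For k = 4: λ = 0.1386 and k^-0.6 = 0.4353. Early: 0.24 × 0.1853/0.5545 = 8.0%. Late: 0.24 × 0.5647/0.8318 = 16.3%. Equal weights give 12.2%.

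| k (assumed) | 2-6 h | 6-12 h | Combined 50/50 |
|---|---|---|---|
| 1 (flat) | 24.0% | 24.0% | 24.0% |
| 2 | 13.8% | 19.6% | 16.7% |
| 4 | 8.0% | 16.3% | 12.2% |
| 8 | 4.7% | 13.7% | 9.2% |

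CSF/Cmin is 24% in every row by construction. Even the 6-12 h mean falls short of it, so splitting by interval does not by itself recover CSF/Cmin.

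**Step 3: dependence on the mix.** At k = 4, 25% early and 75% late gives 0.25 × 8.0 + 0.75 × 16.3 = 14.2%. The reverse mix gives 10.1%. Two groups with those opposite mixes would differ by a factor of 14.2/10.1 = 1.4 with no difference in penetration.

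**Step 4: if CSF is not constant.** If CSF falls in step with plasma and is 24% of it throughout, the paired ratio is 24% at every time and the CSF trough is 24% of Cmin, so on that reading the gap vanishes. CSF at the sampling times over Cmin would then average 36%, 46% and 64% for k = 2, 3 and 5. Hypothesis 1 does not say which CSF level is meant.

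**Step 5: direction.** Item 6 is written as plasma to CSF, so 24% corresponds to 1/0.24 = 4.17. Arithmetic means do not invert: at k = 3 the combined mean plasma:CSF ratio is 8.0, whose inverse is 12.5%, while the mean CSF:plasma ratio is 13.8%. Geometric means do invert.

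**The case against.** Item 6 does match its own objective and endpoint. Objective 1.2.5 asks for CSF concentrations relative to plasma and does not mention Cmin, and endpoint 4 is the paired ratio. The mismatch is with one approximate hypothesis for which no test or decision rule is planned. That stands, and it limits how much weight the point can bear. Section 3.2 does name CSF maraviroc concentration as a primary outcome of the sub-study, but section 9 treats it as secondary and largely descriptive, in a pilot.

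Several stronger readings are tempting, and the documents do not support them:

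- **That the plan pools all samples over 2-12 h.** Item 6 summarises by week and is silent on post-dose interval. It neither combines the intervals nor rules out showing them separately.
- **That the sub-study cannot address its 24% figure.** The limitation is in the item 6 summary. Sampling times are spread to support population PK modelling, which could supply Cmin, and some samples may fall near the end of the interval. What is missing is the text in section 9.
- **That the paired ratio would read 12%, 6% or 3%.** Those values are 0.24 divided by 2, 4 or 8, and apply only if every sample sits at that multiple of Cmin. Half the sampling is planned for 6-12 h. Under the step 2 assumptions, a combined 6% would need about a 29-fold fall from 2 to 12 h, and 3% about an 820-fold fall.
- **That the regimen comparison is confounded.** This would require sampling times to differ between PI/r and NNRTI groups. Nothing indicates that they will, although the planned balance is not set within regimen.

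**Conclusion.** The point holds as a mismatch of definition. Hypothesis 1 concerns CSF relative to plasma Cmin, and item 6 summarises a near-simultaneous paired ratio by week without regard to time since dose. The two coincide only with flat plasma or all-trough sampling, and the planned timing makes the second unlikely. This conclusion does not rest on an assumed profile.

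The size does. With log-linear plasma, constant CSF at 24% of Cmin and equal windows, a combined CSF:plasma ratio of about 16.7%, 12.2% or 9.2% would appear for a 2-, 4- or 8-fold fall. The fold values are assumptions. Constant CSF is a simplification that hypothesis 1 itself does not make, and the gap narrows as CSF tracks plasma. A reader should not infer that the sub-study is unable to inform the 24% figure, or that the regimen comparison is biased. Severity is minor: no alpha, sample size or primary conclusion of the main trial changes.

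**What to change.** Amend item 6 as follows.

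1. Report the paired ratio as CSF:plasma, to match the hypothesis, on the log scale (geometric mean, 95% CI), separately for 2-6 h and 6-12 h at each week.
2. Set 24% only against samples near the end of the dosing interval, with the time cut-off stated in advance, or against CSF/Cmin from the population PK model mentioned in section 3.2. In the second case, specify the model in section 9, label the result as secondary and model-dependent, and carry the uncertainty in predicted Cmin into the interval. State which CSF level the hypothesis means.
3. Include time post-dose in the PI/r v NNRTI comparison, for example in a linear model for the log ratio. Neither of the tests named in item 6 takes a covariate.
4. Confirm that dose and sampling times are recorded. Sections 6.3.13 and 6.3.14 do not say so.

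**Cost.** Items 1 and 3 are a cheap improvement: analysis wording and no new samples. The price is fewer samples per interval and wider intervals. At week 4, 17 subjects give about 17/2 = 8.5 pairs per window. If the average of 2.5 LPs includes one pre-treatment LP, on-drug pairs total about 17 × 1.5 = 25.5, leaving 25.5 − 17 = 8.5 at week 24, or about four per window; individual values should be shown there. The model-based part of item 2 is not a short calculation. The entry draw precedes the first dose (6.2.1), so each subject has at most two on-drug plasma samples, in up to 17 subjects over three dose groups (5.1.1).
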